### **Data collection and analysis**

Patients in the pre-intervention period will be retrospectively identified from microbiological data. All isolates of *Clostridium difficile* from 2015 (and 2014, if necessary) will be revised backwards to choose comparable patients with those included in the prospective period, according to the severity of the first episode.

Data will be collected from electronic medical records which include daily medical evaluations and daily treatments administered to the patient.

Patients in the intervention period will be identified by daily reporting of positive tests for CDI from the Microbiology laboratory and prospectively followed by a member of the research team.

The variables will be collected in a coded database for further analysis.

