## **Patients selection and follow-up:**

The first 100 patients fulfilling the inclusion criteria will be included in the prospective phase of the study. Patients will be identified by means of daily report of the positive results from the Microbiology lab. They will be prospectively followed 8 weeks after the end of treatment for the episode of CDI. If there are one or more recurrences, the follow-up will endure until 8 weeks after the end of the last CDI treatment.

They will be retrospectively compared with patients diagnosed with a first episode of CDI during the previous year (2015) in which there was not a systematical intervention by a member of the Infectious Diseases Unit.

To ensure comparability, patients from the retrospective period will be chosen and matched with patients included in the prospective period according to the severity of the initial episode of CDI and to the Charlson Age-Comorbidity Index (CACI).

If patients diagnosed during 2015 are not enough to fulfil those comparison criteria, we will search backwards through patients diagnosed with a first episode of CDI during 2014 to be matched.

The retrospective follow-up will also endure until 8 weeks after the end of the last CDI treatment.

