## **Definitions:**

**Diarrhoea:** Loose stools, i.e. taking the shape of the receptacle or corresponding to Bristol stool chart types 5–7, plus a stool frequency of three stools in 24 or fewer consecutive hours or more frequently than is normal for the individual.

An **episode of CDI** is defined as: A clinical picture compatible with CDI and microbiological evidence of free toxins and the presence of *C. difficile* in stool without reasonable evidence of another cause of diarrhoea or Pseudomembranous colitis as diagnosed during endoscopy, after colectomy or on autopsy.

**Mild or moderate CDI/non-severe CDI:** Diarrhoea without systemic symptoms, leukocytosis with a white blood cell count lower than 15,000 cells/mL and a serum creatinine level less than 1.5 times the premorbid level.

**Severe CDI:** systemic symptoms of infection and/or leukocytosis with a white blood cell count of 15,000 cells/mL or higher or a serum creatinine level greater than or equal to 1.5 times the premorbid level.

**Severe Complicated CDI/Fulminant CDI:** was defined by the presence of severe disease accompanied by life-threatening conditions such as ileus, toxic megacolon, refractory hypotension and/or multi-organ failure attributable to CDI.

**Ileus:** Signs of severely disturbed bowel function such as vomiting and absence of stool with radiological signs of bowel distension.

**Toxic megacolon:** Radiological signs of distension of the colon (>6 cm in transverse width of colon) and signs of a severe systemic inflammatory response (nausea, vomiting, dehydration, lethargy or tachycardia addition to fever and abdominal pain).

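### Past controls are matched from records that already hold their recurrence outcome, and the plan neither settles which of several matching patients is taken nor keeps recurrence out of the choice

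*Combined protocol and SAP*

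**What the plan says.** Intervention patients enter by a consecutive rule: the first 100 who meet the criteria, from 1 February 2017 (Inclusion criteria; Patients selection and follow-up).

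Controls are handled differently. Under Patients selection and follow-up they are matched to intervention patients "according to the severity of the initial episode of CDI and to the Charlson Age-Comorbidity Index (CACI"). The same section sets the order of years: "If patients diagnosed during 2015 are not enough to fulfil those comparison criteria, we will search backwards through patients diagnosed" in 2014. Their follow-up is read from the past: "The retrospective follow-up will also endure until 8 weeks after the end of the last CDI treatment".

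Data collection and analysis describes how this is done. Isolates from 2015, and from 2014 if needed, "will be revised backwards to choose comparable patients with those included in the prospective period, according to the severity of the first episode". CACI is not named there. The source is the full chart: "Data will be collected from electronic medical records which include daily medical evaluations and daily treatments administered to the patient".

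The document gives no CACI tolerance, no rule for taking one patient when several fit, no masking of the person who selects, and no locking of pairs before outcomes are read. The coded database (Data collection and analysis) and the restricted access to it (Ethical aspects) protect confidentiality. They do not separate selection from outcome.

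**The concern.** Reducing recurrence is the primary objective, and the chosen controls supply the whole comparison rate. The choice is made from records in which each candidate's recurrence status can already be read. If two or more past patients fit an intervention patient, and the person choosing knows who recurred, the choice can drift with the outcome without any intent. A drift towards patients who recurred inflates the apparent benefit of the bundle; a drift the other way hides a real one.

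The conditional logistic model adjusted for confounders (Statistical Plans) does not protect against this. Adjustment can balance measured baseline factors, but it cannot undo selection on the outcome itself.

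**Working it through.** **Is the outcome on file when controls are chosen?** Take the latest first episode in the main control year, 31 December 2015, with a 14-day course. That is the upper end of the range in the Hypothesis section for mild or moderate disease, used here only to date the window. Adding 14 + 56 = 70 days gives 10 March 2016, which is 328 days before 1 February 2017.

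The source list may show recurrence too. All isolates of the year are reviewed, and an episode is normally defined by "A clinical picture compatible with CDI and microbiological evidence of free toxins and the presence of" the organism in stool. A recurrence would therefore usually add a second entry for the same patient. This is an inference: the plan does not say whether the selector sees repeat entries.

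**What is fixed and what is open?**

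| Element | Status in the plan |
|---|---|
| Matching factors | Severity and CACI in one section; severity only in the other |
| Order of years | 2015, then 2014 |
| Order within a year | *Backwards*, not stated as a selection rule |
| CACI tolerance | Not given |
| Choice when several fit | Not given |
| Selection kept apart from recurrence | Not given |

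**Inputs for an illustration.** From Statistical Plans: 99 per group, control recurrence p1 = 0.276, target reduction 0.15 (so 0.126 under the alternative), two-sided 0.05.

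The plan's 99 does not follow from these inputs. With mean proportion 0.201, the pooled formula gives [1.96 × √(2 × 0.201 × 0.799) + 0.8416 × √(0.276 × 0.724 + 0.126 × 0.874)]² / 0.15² = 111 per group, and 99 gives about 75% power. That is a separate matter. Here 99 is used only as the planned size.

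**Model.** One control per intervention patient, members of a pair independent (an assumption). A swap replaces a matching control without recurrence by an equally matching one with recurrence; a negative number means the reverse.

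- Recurrent controls: X ~ Bin(99, p1); after k swaps X′ = X + k.
- Pairs with only the control recurrent: b ~ Bin(X′, 1 − p2).
- Pairs with only the intervention patient recurrent: c ~ Bin(99 − X′, p2).
- Uncorrected McNemar: z = (b − c)/√(b + c); significant in favour of the bundle if z > 1.96.

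**No true effect, p1 = p2 = 0.276 (exact enumeration):**

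| Swaps | Shift in control rate | Chance of a significant result favouring the bundle |
|---|---|---|
| 0 | 0 | 2.46% |
| 1 | 1/99 = 1.0 point | 3.45% |
| 2 | 2/99 = 2.0 points | 4.74% |
| 3 | 3/99 = 3.0 points | 6.40% |
| 5 | 5/99 = 5.1 points | 11.05% |

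Other paired tests show the same pattern. From 0 to 5 swaps, the continuity-corrected McNemar test goes from 1.66% to 8.25%, and the Wald test of an unadjusted conditional logistic model, log(b/c)/√(1/b + 1/c), from 2.30% to 10.43%.

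**True reduction, p1 = 0.276, p2 = 0.126:** five swaps the other way (k = −5) cut power from 76.0% to 46.1% (uncorrected McNemar).

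**Dependence on the pool.** With no surplus candidates the shift is zero. With one surplus candidate, the chance that the first is non-recurrent and the second recurrent is 0.724 × 0.276 = 0.1998. If the recurrent one were then always taken, three expected swaps need 3/0.1998 ≈ 15 such pairs and five need about 25. If it were taken half the time, about 30 and 50. The first case is close to deliberate selection and serves as an outer bound.

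**The case against.** **A selection order may already be implied.** Both sections speak of working backwards. If that means reverse-date order with the first match taken, little discretion is left. This stands in part. A reader might infer that the plan has no rule at all, and that would be wrong: the matching factors, the order of years and a hint of review order are there. But the plan does not say that the first match is taken, and without a CACI tolerance even who counts as a match is open.

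**The harm is conditional.** Nothing suggests that recurrence would steer the choice, the number of surplus candidates is unknown, and the plan itself foresees that 2015 may be too small. All of this stands. The 2014 fallback, however, also enlarges the pool.

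**The swap counts are arbitrary.** True, and so is the single direction. One or two swaps move the error rate only modestly.

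**Historical controls always have outcomes on file, and the study is called exploratory.** Both true. But the plan also sizes a two-sided 0.05 comparison, and selection can be kept apart from outcome even in a historical design.

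**The two sections conflict.** A reader might infer this because one names CACI and the other does not. It is an omission to be aligned, not a contradiction.

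**Conclusion.** The point holds as an unguarded opportunity and calls for a cheap improvement. Controls are chosen after their outcomes are recorded, the choice among matching patients is not fully specified, and nothing keeps recurrence out of it.

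A reader might go further and conclude that the control rate will be biased, or biased in favour of the bundle. The documents do not support that: they show no outcome-related choice, the direction could be either, and the effect is nil if each intervention patient has only one possible match.

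The size cannot be estimated from the documents. The figures show sensitivity only. They rest on 99 independent pairs, the plan's 27.6% and 15-point assumptions, an unadjusted paired test, and swaps all in one direction.

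**What to change.** 1. Add CACI to Data collection and analysis so that it agrees with Patients selection and follow-up.

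2. Before any recurrence data are abstracted, list all eligible first episodes of the control period with only date, eligibility, severity and CACI.
   - The index episode should be the first positive test that meets the plan's own episode definition and has no earlier CDI episode on record. The first positive test alone will not do: Secondary objectives recognises colonised patients without symptoms, and Microbiological methods accepts toxin-negative samples confirmed by PCR, so an early positive could misdate or lose the true first episode.
   - Take severity from an index-episode window stated in advance. The plan gives a window for the white-cell count only, while severe disease is defined by "systemic symptoms of infection and/or leukocytosis with a white blood cell count of 15,000 cells/mL or higher or a serum creatinine level" criterion, so the other components need one too.

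3. Match exactly on severity and to the nearest CACI within a tolerance stated in advance. Break ties at random with a recorded seed, or by a stated reverse-date order if that is what is meant. Keep the 2015-then-2014 order. Lock the pairs, then abstract recurrence.

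4. Report eligible candidates per year and unmatched intervention patients.

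**Cost.** Severity and CACI must be abstracted for every candidate, not only those chosen. Masking is only partial if one person does both steps in the same record system. A tolerance may lose pairs: falling from 99 to 89 lowers power from 76% to 72% in the model above, although the 2014 fallback may limit this.

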### **Statistical Plans**

We present an exploratory study which aim is to evaluate the impact of an intervention, consisting on a bundle of measures for patients diagnosed with a first episode of CDI. The bundle includes antimicrobial stewardship, close follow-up, optimization of specific treatment for CDI and potential search for clinical and biological markers of recurrence. The required sample size was estimated under the hypothesis that the application of a strategy based on a bundle to improve the management of CDI, would decrease the risk of recurrence as compared to the usual care performed in the retrospective period.

A recent review that evaluated the frequency of treatment failure and recurrence of CDI showed a recurrence rate after metronidazole treatment of 27.6% in studies performed in Europe during the previous 10 years.

Based in the previous literature, we expected a cumulative incidence of recurrence in the control group of 27.6%. The study would require a sample size of 99 for each group (i.e. a total sample size of 198, assuming equal group sizes), to achieve a power of 80% for detecting a reduction in proportions of 0.15 between the two groups (reference group - intervention) at a two sided p-value of 0.05.

1. Vardakas KZ, Polyzos KA, Patouni K, Rafailidis PI, Samonis G, Falagas ME. Treatment failure and recurrence of *Clostridium difficile* infection following

treatment with vancomycin or metronidazole: a systematic review of the evidence. *Int J Antimicrob Agents* 2012; 40:1–8.

2. Ralph B. D'Agostino, Sr, Sylva H. Collins, Karol M. Pencina, Yin Kean, and Sherwood Gorbach. Risk Estimation for Recurrent *Clostridium difficile* Infection Based on Clinical Factors. *Clinical Infectious Diseases* 2014 58: 1386-1393.

The data of qualitative variables will be expressed as absolute values and relative frequencies. The data of quantitative variables will be shown as mean  $\pm$  standard deviation should be demonstrated normal distribution or median with interquartile range otherwise. Categorical variables will be compared using  $\chi^2$  or Fisher's exact test for paired samples. Continuous variables will be compared using the Student's t-test or the Mann-Whitney U test for paired samples.

The impact of our intervention will be analyzed as a categorical variable and will be entered as a predictor variable into a conditional logistic regression model, adjusted by potential confounding factors. Associations will be given as relative risks.

A set of sensitivity analyses will be explored by restricting the overall cohort according to the type of episode (first episode versus recurrence) and by hospital ward (medical versus surgical).

Statistical analysis will be conducted using SPSS version 22.0 (SPSS Inc, Chicago, Illinois, USA).

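### The stated inputs (27.6% control recurrence, reduction 0.15, two-sided 0.05, 80% power) need 109 to 111 patients per group, not 99, and no within-pair correlation is given that would justify 99 for the matched analysis

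*Combined protocol and SAP*

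**What the plan says.** The Statistical Plans section takes the control rate from a published review: "we expected a cumulative incidence of recurrence in the control group of 27.6" per cent. It gives 80% power "for detecting a reduction in proportions of 0.15 between the two groups (reference group - intervention) at a two sided p-value of 0.05". The conclusion is: "The study would require a sample size of 99 for each group (i.e. a total sample size of 198, assuming equal group sizes"). It names no formula, software, within-pair correlation, discordant-pair proportion or allowance for non-evaluable patients.

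Two other places bear on the figure. Under Patients selection and follow-up, "The first 100 patients fulfilling the inclusion criteria will be included in the prospective phase of the study", and "patients from the retrospective period will be chosen and matched with patients included in the prospective period", on severity of the initial episode and the Charlson Age-Comorbidity Index. In Statistical Plans, the comparative tests are described as being for paired samples, and the intervention "will be entered as a predictor variable into a conditional logistic regression model, adjusted by potential confounding factors".

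**The concern.** The paragraph supplies every input of a standard comparison of two independent proportions, so its result can be checked directly, and 99 per group is lower than those inputs require. It describes two groups of equal size and mentions neither pairs nor discordance, although the analysis is matched. A reader therefore cannot tell which of two things the 80% refers to: an unpaired test, where it is not reached, or a matched test, where it may be reached but an essential input is missing.

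This is the plan's only justification of its size, and it concerns the primary outcome, recurrence. If the study finds no difference, readers will judge that result against a stated 80% power that the printed inputs do not deliver.

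**Working it through.** **Inputs (Statistical Plans).** Control p1 = 0.276. Reduction d = 0.15, so p2 = 0.126. Two-sided α = 0.05 (z = 1.960), power 80% (z = 0.842), equal groups. (1.960 + 0.842)² = 7.849 from unrounded values. p1(1−p1) = 0.199824 and p2(1−p2) = 0.110124, sum 0.309948. Mean proportion 0.201, so 2 × 0.201 × 0.799 = 0.321198.

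**Step 1. Attempt to reproduce 99, unpaired.**

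| Method | Calculation | n per group |
|---|---|---|
| Unpooled variance | 7.849 × 0.309948 / 0.15² | 108.1 → 109 |
| Arcsine | 2 × 7.849 / 0.3805², with 0.3805 = 2·asin√0.276 − 2·asin√0.126 | 108.4 → 109 |
| Pooled variance under the null | (1.960√0.321198 + 0.842√0.309948)² / 0.15² | 110.9 → 111 |
| Pooled with continuity correction | (110.86/4) × [1 + √(1 + 4/(110.86 × 0.15))]² | 123.8 → 124 |

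Pooled variance in both terms gives 113. No two-sided variant gives 99. One-sided formulas give 88, or 101 with a continuity correction, but the plan states a two-sided test.

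**Step 2. Unpaired power at the planned size.** Unpooled, n = 99: 0.15/√(0.309948/99) − 1.960 = 0.721, so power is 76.4%. Pooled, n = 99: (0.15√99 − 1.960√0.321198)/√0.309948 = 0.686, so 75.4%.

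| n per group | Pooled | Unpooled | Chi-square test, exact enumeration |
|---|---|---|---|
| 99 | 75.4% | 76.4% | 76.6% |
| 100 | 75.8% | 76.9% | 76.9% |
| 109 | – | – | 80.3% |

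With 99 per group, 80% power is reached for a reduction of 0.156 (unpooled) to 0.158 (pooled).

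**Step 3. The matched analysis.** With within-pair correlation φ, the probability that both members of a pair recur is p11 = p1p2 + φ√[p1(1−p1)p2(1−p2)]. The discordant-cell probabilities are p1 − p11 and p2 − p11. The plan states no φ, so 0 to 0.2 is an assumed range. Power for 99 pairs was enumerated over the number of discordant pairs, with intervention as the only covariate.

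| φ (assumed) | Discordant cells | Conditional logistic, Wald | Conditional logistic, likelihood ratio | McNemar chi-square | Exact McNemar |
|---|---|---|---|---|---|
| 0 | 0.2412 / 0.0912 | 74.4% | 76.4% | 76.0% | 69.2% |
| 0.10 | 0.2264 / 0.0764 | 78.7% | 80.8% | 80.6% | 73.7% |
| 0.20 | 0.2116 / 0.0616 | 83.2% | 85.3% | 85.3% | 78.9% |

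Power of 80% needs φ of about 0.08 (likelihood ratio), 0.09 (McNemar chi-square), 0.13 (Wald) or 0.22 (exact).

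**Step 4. Possible origins of 99.**
- Closed-form McNemar formula, with pd the sum of the discordant cells: [1.960√pd + 0.842√(pd − d²)]²/d². It gives 113.6 pairs at φ = 0, 103.2 at φ = 0.10 and 98.06 at φ = 0.15, the last rounding up to 99.
- 27.6% versus 12.0%, unpooled: 7.849 × (0.199824 + 0.1056)/0.156² = 98.5, which also rounds up to 99. The reduction is then 0.156, which would print as 0.16.
- The pooled two-sided formula with 75% power in place of 80% gives 99.

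The plan documents none of these.

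**The case against.** The strongest reply is that the study is matched throughout: matched selection, tests for paired samples, conditional logistic regression. A paired calculation would be the natural one, and a McNemar formula with correlation 0.15 does give 99. On that reading 99 is not a wrong number; one input was left out. That possibility stands, and it is why this point does not claim that the matched study is underpowered. It does not rescue the paragraph. The printed wording describes a comparison of two equal groups, and if a correlation was used, the decisive input is absent.

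Rounding is a second reply. A reduction of 0.1549 would still print as 0.15 and needs 100.2 (unpooled) or 102.9 (pooled) per group, which round up to 101 and 103. That closes most of the gap but does not reach 99, and it assumes the most favourable unrounded value.

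Third, the study is called exploratory, the unpaired shortfall is about 3 to 5 percentage points of power, and nothing in its conduct depends on 99 rather than 109. All true. This bears on how much is at stake and on the remedy, which should be wording only; it does not make the figures agree.

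Finally, the correlations above are assumed, and they describe a model without the planned confounder adjustment. That is correct, and any text that uses them must say so.

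**Conclusion.** The concern holds. With the stated inputs, 99 per group does not give 80% power in an unpaired two-sided test: 109 to 111 per group are needed without continuity correction, and power at 99 is 75.4% to 76.6%. Enrolling 100 does not close the gap. This part uses only the plan's own figures.

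For the planned matched analysis, the stated 80% can be neither confirmed nor refuted. With 99 pairs, conditional logistic regression has 74.4% to 76.4% power at a within-pair correlation of 0, 78.7% to 80.8% at 0.1, and 83.2% to 85.3% at 0.2 (Wald to likelihood ratio). This part rests on an assumed correlation range, complete 1:1 pairs and no covariate adjustment.

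No allowance for non-evaluable patients is stated. Purely as an illustration, 90 evaluable per group would give 71% to 72% unpaired power by the two normal formulas. The practical shortfall is modest, but the printed size, effect and power are inconsistent and should be corrected.

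**What to change.** Keep the enrolment and the analysis, and correct the sample-size paragraph.

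If 99 came from a paired formula or from a different intervention rate, state that formula and input; that alone resolves the point. Otherwise, replace the power statement with text such as:

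> With 99 patients per group, an unpaired two-sided 0.05 test of 27.6% versus 12.6% has about 75% (pooled variance) to 76% (unpooled variance) power. For the planned 1:1 matched analysis with 99 pairs, power is about 74–76% if the within-pair correlation of recurrence is 0, 79–81% if it is 0.1 and 83–85% if it is 0.2 (conditional logistic regression, Wald to likelihood-ratio test, before covariate adjustment; the correlations are assumed). No allowance is made for non-evaluable patients.

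If 80% is to remain the headline, present it as the detectable difference, about 0.157 unpaired with 99 per group, and say that this is not a clinical target.

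The cost is wording only. The downside is a slightly lower stated power, or a range in place of a single figure, in a study already described as exploratory.

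### On the plan's own inputs 99 per group gives about 75% power, not 80%; restate it and, if the 2015 pool allows, pre-specify variable-ratio matching to recover the shortfall

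*Combined protocol and SAP*

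**What the plan says.** All the sample-size inputs are in Statistical Plans:

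- Control rate: "we expected a cumulative incidence of recurrence in the control group of 27.6"%.
- Effect: "detecting a reduction in proportions of 0.15 between the two groups", which implies 12.6% under the intervention.
- Test level: "at a two sided p-value of 0.05".
- Target: "to achieve a power of 80"%.
- Result: "The study would require a sample size of 99 for each group", that is, "a total sample size of 198, assuming equal group sizes".

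Patients selection and follow-up fixes the prospective group: "The first 100 patients fulfilling the inclusion criteria will be included in the prospective phase of the study". The same section matches past patients on severity of the initial episode and on the Charlson Age-Comorbidity Index (CACI), and turns to 2014 if 2015 cannot supply enough matches. Data collection and analysis says that the 2015 isolates, and those from 2014 if needed, "will be revised backwards to choose comparable patients with those included in the prospective period, according to the severity of the first episode"; CACI is not mentioned there. No section gives a number of controls per patient, a CACI tolerance or a count of eligible past patients. The main analysis is a conditional logistic regression. Ethical Aspects says a consent waiver will be requested for the pre-intervention group.

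**The concern.** There are two linked problems.

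First, the stated power does not follow from the stated inputs. A reader would judge a null result against a promised 80%, when the design as sized offers about 75%.

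Second, equal groups suit a study in which both groups cost about the same to recruit. Here they do not. Each intervention patient needs consent, expert assessment and prospective follow-up, and the number is fixed at 100. Controls are abstracted from electronic records. Control numbers are therefore the natural place to look for the missing power, and the plan neither considers this nor fixes a ratio.

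**Working it through.** **Inputs** (Statistical Plans): p0 = 0.276, p1 = 0.276 − 0.15 = 0.126, two-sided alpha 0.05 (z = 1.960), power 0.80 (z = 0.842). The number of intervention patients, 100, is from Patients selection and follow-up.

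**Step 1: try to reproduce 99 per group.** With equal groups and pooled variance under the null:

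n = [1.960·√(2·p̄·q̄) + 0.842·√(p0q0 + p1q1)]² / 0.15²

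- p̄ = 0.201, so √(2 × 0.201 × 0.799) = 0.5667
- √(0.1998 + 0.1101) = 0.5567
- n = (1.1108 + 0.4686)² / 0.0225 = 110.9, so **111 per group**

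Other two-sided versions also miss 99: unpooled 109, arcsine 109, continuity-corrected 124. One-sided versions give 88, or 101 with continuity correction, but the plan says two-sided. The pooled formula returns 99 when power is set to 75%.

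**Step 2: power at the stated size.** Power = Φ[(0.15·√n − 1.1108) / 0.5567].

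- n = 99: Φ(0.3817 / 0.5567) = Φ(0.686) = **75.4%**
- n = 100: Φ(0.3892 / 0.5567) = Φ(0.699) = **75.8%**

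Exact enumeration at 99 per group gives 76.6% for the Pearson test and about 70.3% for Fisher's test.

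**Step 3: a paired calculation.** McNemar's formula needs 114 pairs when within-pair correlation is zero. It needs 101.2 pairs at a correlation of 0.12 and 98.1 at 0.15, so 99 would require a correlation near 0.14. The plan states none.

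**Step 4: more controls for the same 100 intervention patients.** With m controls:

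- p̄ = (m·p0 + 100·p1) / (m + 100)
- SE0 = √[p̄q̄(1/100 + 1/m)]
- SE1 = √(p0q0/m + p1q1/100)
- Power = Φ[(0.15 − 1.960·SE0) / SE1]

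| Controls | SE0 | SE1 | Power |
|---|---|---|---|
| 100 | 0.057 | 0.056 | 75.8% |
| 129 | 0.054 | 0.051 | 80.1% |
| 150 | 0.053 | 0.049 | 82.4% |
| 200 | 0.051 | 0.046 | 86.0% |
| 300 | 0.049 | 0.042 | 89.9% |

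**Step 5: check on matched sets.** A matched-set score test was simulated with 20,000 replicates and no within-set correlation:

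- All 1:1: about 76%
- 70 sets 1:1 and 30 sets 1:2 (130 controls): 79.1%
- 60 and 40 (140 controls): 80.6%
- 50 and 50 (150 controls): about 82%
- 75 sets 1:1 and 25 sets 1:3 (also 150 controls): 80.2%
- All 1:2: about 86%; all 1:3: about 90%

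The formula is therefore slightly optimistic near 130 controls, and how the extra controls are spread across sets matters a little.

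**Step 6: losses (assumed, since the plan gives no allowance).** By the pooled formula, 90 evaluable intervention patients give 71.3% at 1:1, 82.0% at 1:2 and 86.2% at 1:3. With 85 the figures are 68.8%, 79.6% and 84.0%. By simulation, 90 patients with an average of 1.5 controls reach only 76-77%.

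**The case against.** The strongest reply concerns supply. A reader might infer that the plan discards eligible controls whose records are fully worked up anyway. The documents do not support that:

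- The pool size is not given, and Patients selection and follow-up provides for 2015 being insufficient even for the planned matches.
- Reviewing isolates backwards to choose comparable patients is compatible with a search that stops once matches are found.
- Isolates are not yet eligible controls. Recurrences, patients under 18 and those with inflammatory bowel disease must be removed, and nowhere does the plan say that severity and CACI are worked out for every 2015 candidate.
- One-to-one matching is only implied by the equal-size assumption.

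This objection stands. It makes the gain conditional on supply, but it does not rescue the 80% figure.

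The second reply is that matching can raise power, so 99 pairs might suffice. That is arithmetically possible at a correlation near 0.14, but the plan states no such assumption.

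The third is that the study is declared exploratory and equal matched groups are a legitimate choice. That is fair. Even so, the plan states a power figure, and it should follow from its inputs.

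**Conclusion.** The stated power is wrong on the plan's own inputs: about 75-76% at 99-100 per group, against 80% claimed, with 111 per group needed at equal sizes. That rests only on figures in the document and an unpaired calculation, or a paired one without within-pair correlation.

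The remedy through extra controls is real but conditional. About 130-150 controls for 100 intervention patients would bring power to about 80-82%, and 200 to about 86%. This assumes that enough comparable 2015 patients exist, that match quality is kept, and that all 100 intervention patients are matched and evaluable.

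Two stronger readings go too far. Extra matching cannot be said to restore 80% with certainty, because supply is unknown. Nor does it add no participants: it adds no prospective patients, but the data of more past patients would be used under a waiver still to be granted. More controls also narrow the interval without reducing before-after bias.

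**What to change.** 1. In Statistical Plans, restate the power as about 75-76% for one-to-one matching with 99-100 per group, and note that 111 per group would be needed for 80%. If a within-pair correlation was assumed, state and justify it.
2. Before abstracting any control outcomes:
   - count the eligible first-episode patients of 2015;
   - fix one severity rule and one CACI tolerance, worded identically in both sections that describe the matching;
   - pre-specify up to three 2015 matches per intervention patient, each control used once, with 2014 used only for patients who have no 2015 match;
   - restate power for the ratio achieved and for a plausible number of evaluable patients.
3. Analyse by matched set. The conditional logistic regression needs no change of method for this, but the simple paired tests need matched-set versions.

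If the pool is small, matching stays at 1:1 and only item 1 changes the stated result.

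**Cost:** chart abstraction for about 30-100 more records (up to 200 if every patient had three matches), each followed to eight weeks past the final CDI treatment course and covered by the waiver request. The ratio will vary between sets, and second or third matches could be looser unless the tolerance is enforced.
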